When specimens or data collected by research collaborators outside Partners will be sent to Partners investigators, indicate from where the specimens/data will be obtained and whether the specimens/data will contain identifiers that could be used by Partners investigators to link the specimens/data to individual subjects. When appropriate, submit documentation of IRB approval and a copy of the IRB-approved consent form from the institution where the specimens/data were collected.

Not applicable.

Protocol Biostatistical Analyses

Separate analyses will be conducted for the 3 endpoints and for the 2 nutritional supplements, vitamin D and omega-3 fatty acids. Analyses of treatment effects will be based on the intent-to-treat principle. The first analysis will compare baseline characteristics by randomized treatment

assignment to ensure that balance was achieved by the randomization. Characteristics to be examined include known risk factors for autoimmune diseases, systemic inflammation, and chronic knee pain including: age; gender; race/ethnicity; family history of autoimmune disease; BMI; smoking; alcohol use; physical activity; co-morbid medical conditions such as hypertension, hyperlipidemia, diabetes, and cardiovascular disease; and baseline vitamin D and omega-3 fatty acid levels as assessed by dietary questionnaire in all participants and blood assays in the case-cohort subsample. The large sample size, as well as successful balance of known potential confounders, will provide assurance that unmeasured or unknown potential confounders will also be equally distributed across randomized treatment groups. For autoimmune disease, we will estimate the intervention effects on the primary endpoint of total incident autoimmune disease. For inflammatory biomarkers, we will assess changes in linear biomarkers (log transformed if necessary). For chronic knee pain, the primary endpoint will be assessed by the WOMAC pain scale; secondary analyses will test for decreases in WOMAC stiffness, function and global scales, as well as analgesic use separately. Data analyses will be performed using SAS 9.2 (SAS Institute Inc., Cary, North Carolina).

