Autoimmune Disease Incidence. In this 2x2 factorial design, the primary aim is to compare the main effects of intention-to-treat with vitamin D and with fish oil upon autoimmune disease incidence. Initially, we will compare Kaplan-Meier curves to graphically display the survival functions across different treatment groups and a log-rank test to test the difference. We will use Cox proportional hazards models to assess the main and interaction effects of the treatment groups. The unadjusted risk ratios and their 95% CIs will be used to measure the strength of risk across different treatment groups. The proportional hazard assumption will be tested based on the smoothed plots of the scaled Schoenfeld residuals³⁸⁶. To estimate the cumulative incidence function, a nonparametric estimate will be obtained using the Kaplan–Meier method. Given randomization and blinding of 20,000 individuals in this RCT, most important covariates will be equally distributed. But, in secondary analyses, we will assess the effects of controlling for age, sex and other possible strong predictors, such as family history of autoimmune disease; baseline levels of inflammatory biomarkers, vitamin D, EPA and DHA; dietary vitamin D, EPA and DHA intake; BMI and physical activity.

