Secondary Analyses. Beyond the primary analyses, we will examine several pre-specified secondary outcomes for autoimmune diseases, inflammatory biomarkers, and chronic knee pain. We will examine effect modification by the other randomized intervention, by baseline risk factors, and by time. Given past studies showing interactions between intake of n-6 fatty acids and n-3 in reductions in biomarkers of systemic inflammation²⁸⁵, we have a particular interest in exploring interactions between the interventions, as well as with the baseline plasma biomarkers of 25(OH)D for vitamin D and of EPA+DHA for fish oil, and dietary intake of both. We hypothesize that the intervention effects may be larger among those with below-median baseline levels and will examine treatment effects by quartiles of these biomarkers. When stratifying by 25(OH)D, season (assessed by date of return) and geographic location (assessed by zip code) will be considered. We also have a prior interest in the effects of the vitamin D intervention within groups defined by race/ethnicity and skin pigmentation, and by BMI. In addition, we will evaluate effect modification by age and gender, as well as by sunlight exposure, calcium and phosphorus intakes from the FFQ (as these nutrients affect vitamin D bioavailability¹), and baseline risk factors for autoimmune disease, systemic inflammation and chronic knee pain. Interaction effects will be interpreted cautiously, as hypothesis-generating. Finally, we will examine whether treatment effects vary over time and duration of treatment by examining survival plots and interactions with time. There may be latent effects on outcomes, depending on the stage at which these agents act.

Analysis of potential adverse effects. We will also compare the incidence of potential side effects in the active vs. placebo groups for each agent, including the incidence of kidney stones with vitamin D assignment³⁸⁹ and the incidence of GI symptoms, skin abnormalities, and bleeding with fish oil assignment.³²⁹

Power calculations. This section provides a detailed power analysis for each of the 3 aims. To calculate

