power, the following assumptions were made: (1) a 2x2 factorial trial in 10,000 men aged ≥ 60 and 10,000 women aged ≥ 65 ; (2) independent and equal allocation of participants to each treatment in the trial (for Aim 1); (3) an age distribution based on that observed at baseline in our past RCTs for men aged ≥ 60 and women aged ≥ 65 ; (4) trial follow-up of 5 years, with little loss to follow-up as achieved in our past RCTs; and (5) compliance of 80% similar to that in published trials upon which our estimated rate ratio (RR) reductions are based. Power calculations were performed using the observed RR, given past observed effects and assuming

a compliance of 80%. The corresponding true relative risk (RR) with perfect compliance is also calculated.

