a. Incident autoimmune diseases. As in **table 1**, we estimate the annual incidence of total autoimmune diseases in a U.S. population over age 60 to be approximately 1000 cases per 100,000 individuals per year: thus, in this trial of 20,000 individuals for 5 years, 1000 incident cases. (**Table 2**) Conservatively, we will validate 60% of these 1000 cases, or 600 cases, with 150 occurring in the placebo group and fewer in the intervention groups if they are effective. Given the clustering of autoimmune diseases within individuals, some incident cases will occur within the same individuals, and these will be analyzed as discrete endpoints. Power is given for a a logrank test³⁹⁰ based on the proportional hazard rates with a significance level of 0.05. (**Table 4**) Assuming that only one agent is effective, with 5 years of treatment and follow-up, we will have 81% power to detect an observed RR of 0.70 (or 30% risk reduction) for the primary endpoint of autoimmune disease incidence. For the secondary endpoint of AITD, we will have 85% power to detect a 40% risk reduction. If both agents are effective in preventing autoimmune disease but act independently, power would be reduced slightly due to a somewhat smaller overall number of events. If the agents interact, however, power will be affected to the extent of the interaction. Should the agents act synergistically, power would increase. For example, if the effect of each agent alone is a reduction of 15%, but in combination the effect is stronger, with an additional 10% decrease, the RR comparing the combined group to the all placebo group would be 0.65, versus 0.72 with additive effects (on the multiplicative scale). Power for the total effects would increase to 91%. Power is shown for a given observed reduction in risk, assuming 80% compliance similar to that seen in trials such as WHS and PHS.

Observed RR†	True RR	Autoimmune Disease	AITD
0.70	0.67	0.81	0.62
0.65	0.61	0.91	0.75
0.60	0.56	0.97	0.85

†Observed RR=intent-to-treat RR assuming compliance 80%. True RR= with perfect compliance. AITD= autoimmune thyroid disease

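### The 91% power quoted for synergy belongs to the combined group against all-placebo; each agent's primary main effect in that scenario is RR 0.81 with about 65% power

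*Combined protocol and SAP*

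**What the plan says.** Under Protocol Biostatistical Analyses, the paragraph on autoimmune disease incidence says that "the primary aim is to compare the main effects of intention-to-treat with vitamin D and with fish oil upon autoimmune disease incidence". The opening paragraph adds: "Separate analyses will be conducted for the 3 endpoints and for the 2 nutritional supplements, vitamin D and omega-3 fatty acids". The interaction between the agents appears under Secondary Analyses: "We will examine effect modification by the other randomized intervention, by baseline risk factors, and by time".

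Item (a) of Power calculations uses a "logrank test³⁹⁰ based on the proportional hazard rates with a significance level of 0.05". It expects 60% of 1000 cases to be validated, "or 600 cases, with 150 occurring in the placebo group and fewer in the intervention groups if they are effective". Allocation is assumed to be "independent and equal allocation of participants to each treatment in the trial (for Aim 1"). For one effective agent it reports 81% power at an observed RR of 0.70.

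It then turns to two effective agents. If they act independently, power is said to fall slightly because there are fewer events overall. If they are synergistic, power is said to rise. In the example each agent alone gives a 15% reduction and the combination a further 10%: "the RR comparing the combined group to the all placebo group would be 0.65, versus 0.72 with additive effects". The example closes with "Power for the total effects would increase to 91"%, which equals the Table 4 entry for RR 0.65. No main-effect RR or main-effect power is given for this scenario.

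**The concern.** The sentence stands in the power paragraph for the primary endpoint and gives a level to which power would increase. The only earlier power figure there for that endpoint is 81%, so a reader will naturally see a rise from 81% to 91% for the planned analysis. But 91% describes one cell of the 2x2 design against another, while the primary tests compare half the trial with the other half.

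In a factorial margin, the effect of one agent is averaged over people who do and do not take the other. The main effect therefore lies between the single-agent effect and the much larger combined effect, and it cannot reach RR 0.65 here. At stake is whether the investigators and the funder believe that modest effects of 15% per agent, with some synergy, would probably be detected by the primary tests. At 65% power, each test would miss the effect about one time in three.

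**Working it through.** **Inputs**
- All-placebo group: 150 validated events (Power calculations, item a).
- Four equal cells, from 20,000 participants with equal allocation.
- Relative risks against all-placebo: 0.85 for each agent alone; 0.85 × 0.85 × 0.90 = 0.65 combined with synergy; 0.85 × 0.85 = 0.7225 combined without it. They are read as observed RRs, with 80% compliance already included, as in Table 4.
- Assumption: two-sided 0.05. Sidedness is not stated for Aim 1.

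**Formulas**

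For event counts a and b in two equal-sized arms:
- direct: z = |ln(b/a)| / √(1/a + 1/b)
- Schoenfeld: z = (√(a+b)/2) × |ln(b/a)|
- power = Φ(z − 1.96)

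**Step 1: reproduce the plan's figures.** Compare one active cell with the all-placebo cell, with 150 against 150 × RR events.

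| RR | Events | Direct | Schoenfeld | Plan |
|---|---|---|---|---|
| 0.70 | 150 v 105 | 0.80 | 0.81 | 0.81 |
| 0.65 | 150 v 97.5 | 0.912 | 0.923 | 0.91 |
| 0.60 | 150 v 90 | 0.969 | 0.977 | 0.97 |

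For RR 0.65: 0.4308 / √(1/150 + 1/97.5) = 0.4308 / 0.1301 = 3.31, and Φ(1.35) = 0.912. The 91% is thus the two-cell contrast, with 247.5 events. A one-sided test does not fit (0.886 and 0.959 at RR 0.70 and 0.65). Nor do the factorial margins (0.981 and 0.998).

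**Step 2: the main effect in the same scenario.** The cell counts derived from the stated 150 are 150 (neither agent), 127.5 (each agent alone) and 97.5 (both).
- Without the agent in question: 150 + 127.5 = 277.5.
- With it: 127.5 + 97.5 = 225.
- RR = 225 / 277.5 = 0.811, with 502.5 events in total.
- Direct: 0.2097 / √(1/277.5 + 1/225) = 0.2097 / 0.0897 = 2.34, power 0.647.
- Schoenfeld: 0.652. The Freedman formula gives 0.649, two proportions 0.660 and a simulation on event counts 0.661.

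**Step 3: the same scenario without synergy.** The combined cell has 150 × 0.7225 = 108.4 events.
- Main effect: 277.5 v 235.9, RR 0.85, z = 1.835, power 0.450 (Schoenfeld 0.453).
- Combined v all-placebo: 150 v 108.4, z = 2.58, power 0.73 (Schoenfeld 0.74).

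**Step 4: sensitivity of the 65%**
- Hazard ratio averaged over strata of the other agent (0.806): 0.675.
- All 600 events kept despite the effect: 0.729 (0.51 without synergy).
- One-sided test, which does not reproduce Table 4: 0.76.

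None of these comes near 0.91.

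**Step 5: Table 4 on the margins, one effective agent.** At RR 0.70 the counts are 300 v 210, and power is about 0.98 (direct 0.977, Schoenfeld 0.981). At RR 0.65 and 0.60 it exceeds 0.99.

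**The case against.** The best defence is that the text names its contrast. It says that 0.65 compares the combined group with all-placebo, and it speaks of total effects rather than main effects. This stands. A reader might infer that 91% is a miscalculation, but the documents do not support that: for the named contrast both the effect size and the power are right.

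A reader might also infer that no comparison of the combined group with all-placebo is planned. That goes too far. The autoimmune analysis paragraph includes a log-rank test and risk ratios across treatment groups, and a Cox model with main and interaction effects, from which this RR could be derived. What can be said is that it is not named as a primary comparison. The Cox model also makes the basis worth stating. With an interaction term in the model, the coefficient for one agent is its effect in the absence of the other (RR 0.85, 127.5 v 150 events), which has only about 27% power.

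Third, it is fair to say that the example is hypothetical, that its direction is correct (45% to 65% for the main effect, 73% to 91% for the combined contrast), and that trial size is set by the parent study. All of this limits the consequence.

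What the defence does not answer is placement. The neighbouring remark, that independent action of both agents lowers power through fewer events overall, makes sense only for marginal comparisons. In a comparison of one agent alone with all-placebo, the other agent changes no event count. The paragraph thus moves between two bases without saying so.

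**Conclusion.** The point holds as a matter of what the figure describes. The 91% is correct for the combined group against all-placebo and does not apply to either primary test. In that scenario each agent's main effect is RR 0.81 with about 65% power, 26 points below the quoted level; the figure is about 73% if no events are lost to the effect. Without synergy it is RR 0.85 with about 45% power.

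These values assume a two-sided 0.05 test (unstated for Aim 1, but the version that reproduces Table 4), 150 events in the all-placebo cell, equal cells, little loss to follow-up, and observed RRs that already include 80% compliance. Only the 150 is the plan's own cell count; the other three are derived from it.

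This does not show that the trial is underpowered in general. For one effective agent at RR 0.70, the two-cell basis of Table 4 understates main-effect power (81% against about 98%). The two discrepancies run in opposite directions and do not cancel, because moving the synergy example to the margins also changes the effect size from 0.65 to 0.81.

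**What to change.** Make three changes in one edit.

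1. In item (a) of Power calculations, say that 91% (about 73% without synergy) is the power for the combined group against the all-placebo group. Add that in the same scenario each agent's main effect is RR 0.81 with about 65% power, or RR 0.85 with about 45% without synergy. State the assumptions: two-sided 0.05, 150 events in the all-placebo cell, and events reduced by the effect, with about 73% (51% without synergy) if all 600 are kept.
2. In the autoimmune analysis paragraph, list the combined against all-placebo contrast as secondary if it is wanted. Say also whether the main effects come from a model without the interaction term.
3. Restate the autoimmune column of Table 4 and the accompanying 81% on the factorial margins (about 98% at RR 0.70 with one effective agent), so that the paragraph does not mix the two bases. Check the thyroid column for the same basis; its event count is not in the text available here.

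Sample size, endpoint and trial conduct do not change. The only downside is that one stated power becomes less favourable, while the single-agent figures become more favourable.

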b. Inflammatory biomarkers. Our power calculations are based on past changes in systemic inflammatory biomarkers in large cohort analyses and we have first assumed that only one agent is effective, that compliance is 80% and that the cohort of 2000 followed over two years for changes in biomarkers is randomly drawn from each of the four treatment groups. (**Table 5**) Based on the distribution of hsCRP, IL-6 and TNFR2, natural log-transformation may be used for power analysis if applicable. According to NHANES 1999-2002

Observed reduction %	hsCRP	IL-6	TNFR2
20	0.72	0.55	>0.99
25	0.89	0.74	>0.99
30	0.97	0.88	>0.99
40	0.99	0.99	>0.99

†Assuming compliance to be 80%.

data, median hsCRP level is 2.8 mg/L for men aged ≥60 and women aged ≥65³⁹¹. Using a two-sided type I error of 0.05, the sample size of 500 patients with compliance of 80% in each group will achieve 89% power to detect a 25% reduction of hsCRP using a two-sided t test (based on log-transformed scale). Pai and

colleagues examined plasma levels of TNFR2 and IL-6 as biomarkers for cardiovascular disease risk among participants in the Nurses' Health Study and the Health Professional Follow-up Study (mean age 60.3 for women, 65.2 for men)¹³⁵. The mean TNFR2 was 2370 pg/ml (SD 795 pg/ml) and the median IL-6 level was 1.6 pg/mL. A sample size of 500 per group with compliance of 80% will achieve more than 99% power to detect 20%-40% reduction of TNFR2 with a two-sided significance level of 0.05. Based on a log-transformed scale, we will have 88% power to detect a 30% reduction in IL-6.

c. Chronic knee pain. In the study by Angst and colleagues, the mean global score was 4.8 and the MCID for improvement in pain was 0.75, for stiffness 0.72, for function 0.67 and for global

	Baseline Score	SD	MCID	Power
WOMAC knee pain	4.83	2.25	0.75	0.99
WOMAC knee stiffness	4.61	2.67	0.72	0.96
WOMAC knee function	4.81	2.18	0.67	0.99
WOMAC Global	4.80	2.09	0.67	0.99

SD= standard deviation per Angst, 2002 MCID= minimally clinically important difference

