score 0.67³⁸⁸. Assuming a type I error rate of 0.05 and a power of 0.80, this translated into sample sizes of 142, 216, 162, and 153 individuals respectively affording adequate statistical power to detect these changes in an RCT of an intervention using the WOMAC as an outcome. We will follow 2000 individuals with chronic daily knee pain longitudinally over up to 5 years. With estimated loss to follow-up and compliance of 80%, we will have generous statistical power to detect the MCID in improvement in WOMAC pain, stiffness, function and global scores. (**Table 6**) Moreover, repeated measurement of WOMAC scores will provide additional power to detect specified effect sizes. Again, unequal group sample sizes could reduce the power to some extent (although is unlikely to occur unless there is a strong chance imbalance). However, if we conservatively assume the intervention to placebo allocation ratio is 1:2, we will still achieve similar power to detect 25% reduction in both inflammatory biomarkers and the WOMAC MCID of knee pain. (The power to detect MCID for WOMAC knee pain would be > 99%, for WOMAC knee stiffness 95%, and for WOMAC knee function 98%.)

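### Table 5's hsCRP and IL-6 powers track the percent reduction itself, not its log-scale equivalent, so they do not match the log-scale t test named; the SDs needed to size the discrepancy are not given.

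*Combined protocol and SAP*

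**What the plan says.** The material is in Protocol Biostatistical Analyses, Power calculations, part b (Inflammatory biomarkers) and Table 5.

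- **Design inputs:** "Using a two-sided type I error of 0.05, the sample size of 500 patients with compliance of 80% in each group".
- **Scale:** the part opens conditionally ("natural log-transformation may be used for power analysis if applicable"), but the two sentences that report power name the scale outright. For hsCRP it is "89% power to detect a 25% reduction of hsCRP using a two-sided t test (based on log-transformed scale"; for IL-6, "Based on a log-transformed scale, we will have 88% power to detect a 30% reduction in IL-6".
- **Marker inputs:** hsCRP has only a median ("median hsCRP level is 2.8 mg/L for men aged" 60 and over and women 65 and over). IL-6 also has only a median ("the median IL-6 level was 1.6 pg/mL"). Neither has an SD on any scale. TNFR2 has both a mean and an SD ("The mean TNFR2 was 2370 pg/ml (SD 795 pg/ml").
- **Table 5, reductions of 20/25/30/40%:** hsCRP 0.72/0.89/0.97/0.99; IL-6 0.55/0.74/0.88/0.99; TNFR2 above 0.99 throughout.
- **Unequal allocation:** the end of part c says of a 1:2 split that "we will still achieve similar power to detect 25% reduction in both inflammatory biomarkers".

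The plan does not say how a percent reduction, or the 80% compliance, becomes a difference on the log scale.

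**The concern.** A t test on log values compares mean logs, so a proportional reduction r enters as −ln(1−r) whatever the marker's level or unit. That function is curved: going from 20% to 30% multiplies r by 1.50 but multiplies −ln(1−r) by 0.3567/0.2231 = 1.60. A column computed with one SD must show that curvature. The hsCRP and IL-6 columns do not; they rise in proportion to r.

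Table 5 is the numerical support for the size of the biomarker subcohort. If the percentage was not converted to a log ratio, the row labels for two of the three markers do not describe the effects that were powered. Without an SD, a reader cannot repair the table.

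**Working it through.** **Formula.** With n per group and a two-sided 0.05 test, power ≈ Φ(d/(SD·√(2/n)) − 1.96). Put z = 1.96 + Φ⁻¹(power). The SD implied by a row is then d·√(n/2)/z. If one SD serves a whole column, z/d is constant down that column.

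**Group size.** I take n = 500 × 0.80 = 400, so √(n/2) = 14.14. This convention fits the knee-pain table: with the SDs and MCIDs given there it yields 0.997/0.968/0.992/0.995, against the printed 0.99/0.96/0.99/0.99. Another n multiplies every implied SD in a column by the same factor and leaves the test of constancy unchanged.

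**What can be reproduced.** TNFR2 at 20%, on the raw scale: 0.20 × 2370 = 474; 474/795 × 14.14 = 8.43; 8.43 − 1.96 = 6.47, so power is above 0.99, as printed. For hsCRP and IL-6 no direct reproduction is possible, so I back-solve. Write δ = −ln(1−r).

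| | 20% | 25% | 30% |
|---|---|---|---|
| δ | 0.2231 | 0.2877 | 0.3567 |
| hsCRP stated power | 0.72 | 0.89 | 0.97 |
| z | 2.543 | 3.186 | 3.841 |
| z/δ | 11.40 | 11.08 | 10.77 |
| z/r | 12.71 | 12.75 | 12.80 |
| implied log SD under δ | 1.241 | 1.277 | 1.313 |
| its rounding band | 1.234–1.248 | 1.266–1.287 | 1.287–1.337 |
| IL-6 stated power | 0.55 | 0.74 | 0.88 |
| z | 2.086 | 2.603 | 3.135 |
| z/δ | 9.35 | 9.05 | 8.79 |
| z/r | 10.43 | 10.41 | 10.45 |
| implied log SD under δ | 1.513 | 1.563 | 1.609 |
| its rounding band | 1.504–1.522 | 1.554–1.572 | 1.596–1.622 |

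Each band uses the printed power ± 0.005.

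**Reading the table.**
- Under δ, the 20% band for hsCRP misses the other two, and all three IL-6 bands are disjoint.
- If the printed powers were truncated instead of rounded, the first two bands are still disjoint: hsCRP 1.227–1.241 against 1.255–1.277; IL-6 1.495–1.513 against 1.544–1.563.
- Compliance outside the log (0.8δ) multiplies every SD by 0.8 and changes nothing. Compliance inside the log, −ln(1−0.8r), still leaves the first two bands apart: hsCRP 0.964–0.975 against 0.982–0.999; IL-6 1.175–1.189 against 1.205–1.219.
- An effect proportional to r fits all three rows of each column with one SD: 1.106–1.119 for hsCRP and 1.350–1.364 for IL-6, taking d = r.
- The 40% row was left out because power is near its ceiling there. For hsCRP either form gives 0.999 or more against the printed 0.99, so it does not separate them.

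**What could give proportionality to r, and the power that follows with the correct shift δ (n = 400):**

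1. *Percentage applied to the log median, d = r·ln(median).* ln 2.8 = 1.030 and ln 1.6 = 0.470. The implied log SD is about 1.14 (hsCRP) and 0.64 (IL-6). Correct power at 20/25/30% is about 0.79/0.95/0.99 for hsCRP and above 0.99 in every row for IL-6.
2. *First-order approximation, d = r.* The implied log SD is about 1.11 and 1.36. Correct power is about 0.81/0.96/0.995 for hsCRP and 0.64/0.85/0.96 for IL-6.
3. *Raw-scale difference, d = r·median.* The implied raw SD is about 3.11 mg/L and 2.17 pg/mL. The percentage labels then stand, the log-scale description does not, and log-scale power cannot be derived.

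**Closest single-SD fit with the correct shift.** hsCRP with SD 1.256 gives 0.710/0.900/0.980, within 1.0 point of the table. IL-6 with SD 1.553 gives 0.529/0.745/0.901, within 2.1 points.

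**The case against.** The strongest reply is that the mismatch is small and the SD is unstated. One SD with the correct shift brings hsCRP within 1 point and IL-6 within about 2, or 1.6 points for IL-6 if compliance sits inside the log. Few design decisions turn on that, and the plan's tables are not strictly rounded: the knee-pain table prints 0.96 where the calculation gives 0.968. This stands as a limit on importance. It does not remove the pattern, which appears in both columns, survives truncation, and disappears once the effect is taken as proportional to r.

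The conditional remark about log transformation could also be read as permitting a raw-scale calculation. That is possible, but the 89% and 88% sentences each state the log scale.

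Stronger readings are tempting, and the documents do not support them:

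- *That the IL-6 row labelled 30% really describes a 13.2% reduction* (1 − 1.6^(−0.30) = 0.132). This holds only if the percentage was applied to the log median. Under the first-order approximation the same row is a 25.9% reduction (1 − e^(−0.30)). Nothing in the plan selects between them.
- *That the 1:2 allocation sentence is shown to be wrong.* Scaling the 25% row for a 1:2 split of the same total gives about 0.85 (hsCRP) and 0.69 (IL-6). But that takes as its start the very row in doubt.

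**Conclusion.** The stated hsCRP and IL-6 powers are inconsistent, at printed precision, with the log-scale t test the plan names. This rests on one SD per column and on the 20%, 25% and 30% rows; it does not depend on n or on how compliance is applied.

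The size of the discrepancy is unknown because the log SDs are not given. It is 1 to 2 points if a single SD with the correct shift is accepted. Under either log-scale explanation the stated powers are too low: hsCRP at 20% would be 0.79 to 0.81 against 0.72, and IL-6 at 20% would be 0.64 to above 0.99 against 0.55. Under the raw-scale explanation log-scale power cannot be derived.

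A reader might infer that Aim 2 is underpowered or that its detectable reductions are wrong. Neither follows: the two explanations that can be quantified make the table conservative, and TNFR2 reproduces. Whether a log SD near 1.26 or 1.55 is plausible needs outside data and was not judged. This is a correction to the power justification for two markers, not a challenge to the design.

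**What to change.** - Recompute the hsCRP and IL-6 columns of Table 5 with the log-scale difference set to −ln(1−r).
- State the log SD used for each marker and its source.
- State how 80% compliance enters: as a smaller effective n, as a multiplier on the log difference, or inside the log.
- If the original calculation was on the raw scale, say so and give that SD, or replace it with the log-scale one.
- Restate the 89% hsCRP and 88% IL-6 sentences, and the biomarker part of the 1:2 allocation sentence, from the recomputed table.

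The cost is a recalculation and a few lines of text. The TNFR2 column, enrolment and procedures do not change.
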